13.2. The number of participants

We estimated the number of participants by calculating the number of participants needed for the three chosen outcomes (bio cellen, bio tyndall and redness of the eye), based on the pilot data. The target p-value was 0.5/3 (=0.0167) in order to correct for multiple testing, and the power was set to 80%. Because we want to see a difference on the three outcomes, we choose the highest sample size estimation, based on the work of Zaho, Rahardja & Yongming (2008), who proposed sample size estimators ordinal data using the Wilcoxon-Mann-Whitney test and available in the R package *sample size*. The percentages for each categories of the ordinal variables by group are used as input for the sample size estimations. The next table presents the results obtained.

	Total by group	Total individuals
Bio cellen	428	858
Bio tyndall	430	860
Redness eye	27	54

Based on this table, a total of 860 patients would be required by group in order to show a difference between 23G and 27G on the three parameters of the outcome: bio tyndall, bio cellen and redness eye.

For each surgical site 25 patients will be recruited by group (i.e. 50 patients will be included at each site).

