13.3. The level of statistical significance

For all analyses, the level of significance will be 5% two-sided significant level. P-values will be adjusted for any multiple comparisons in order to maintain an overall type I error rate of 5%.

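### Section 13.2 ties the sample size to showing a difference on all three outcomes, but its 80% power holds only for each outcome separately, and no decision rule is stated

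*Combined protocol and SAP*

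**What the plan says.** Section 13.2 names three outcomes: cells (bio cellen), flare (bio tyndall) and redness of the eye. On the error rate and power it says: "The target p-value was 0.5/3 (=0.0167) in order to correct for multiple testing, and the power was set to 80" per cent. It sizes each outcome separately with a Wilcoxon-Mann-Whitney formula fed by pilot category percentages. The table gives "Bio cellen 428 858", "Bio tyndall 430 860", and 27 per group (54 in total) for redness. The largest size is chosen for this reason: "Because we want to see a difference on the three outcomes, we choose the highest sample size estimation". The conclusion repeats the aim with a different number: "a total of 860 patients would be required by group in order to show a difference between 23G and 27G on the three parameters".

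Section 13.3 sets the overall level ("the level of significance will be 5% two-sided significant level") and adds: "P-values will be adjusted for any multiple comparisons in order to maintain an overall type I error rate of 5" per cent. It names no adjustment method. Section 13.1 plans one Wilcoxon-Mann-Whitney test per primary outcome. Section 6.1 lists redness and intra-ocular inflammation under the primary endpoint without saying how they combine.

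Recruitment is set elsewhere: 500 patients in total (section 8.1) and 25 per group per site (sections 9.3 and 13.2). Section 13 opens by ruling out pooling across sites, although section 13.1 also plans complementary mixed models across centres.

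**The concern.** The decision rule fixes both the error control and the power, and two rules are mixed here.

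- **A claim on any one outcome, or three separate claims.** Three chances of a false positive call for a split such as 0.05/3.
- **A claim only if all three are positive.** Each test can be run at 0.05 without a split, because a false claim then requires a false positive on an outcome already tested at 5%. The relevant power is the chance that all three tests succeed together, which is normally below the power of the weakest one.

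Section 13.2 uses the split of the first rule, gives its reason in the language of the second, and quotes a power computed one outcome at a time. Two things are at stake. A reader may take 80% as the chance of showing all three differences, which it is not. And with no stated rule, a result positive on redness only, the outcome that needs just 27 per group, could be called success or failure once the data are known.

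**Working it through.** **Inputs.** From section 13.2: 428 (cells), 430 (flare) and 27 (redness) per group, alpha 0.0167, power 80%. From section 13.3: two-sided testing. From sections 8.1, 9.3 and 13.2: 500 patients in total, 25 per group per site. Assumed: the correlation rho between test statistics, shown over a range because the documents give none. No dropout allowance is stated and none was applied.

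**The plan's own figures.** 0.05/3 = 0.0167 matches the printed value; the printed fraction 0.5/3 equals 0.1667 and does not. The sizes cannot be reproduced, because the pilot category percentages are not in the documents, so they are taken as correct. The table's totals agree with twice the group size for flare (2 x 430 = 860) and redness (2 x 27 = 54), but not for cells (2 x 428 = 856, printed 858). The 860 in the concluding sentence is the table's total, not its size by group.

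**Method.** If n0 per group gives 80% power at two-sided 0.05/3, the expected test statistic at n0 is 2.394 + 0.842 = 3.236. At n per group it is 3.236 x sqrt(n/n0). Power for one outcome is Phi(3.236 x sqrt(n/n0) - c), with c = 2.394 at 0.0167 and c = 1.960 at 0.05. Joint power is the multivariate normal probability that every statistic exceeds c.

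**One outcome at a time, alpha 0.0167**

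| Per group | Cells | Flare | Redness |
|---|---|---|---|
| 430 | 80.2% | 80.0% | about 100% |
| 250 | 53% | 53% | about 100% |
| 25 | 5% | 5% | 76% |

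Example, flare at 250: 3.236 x sqrt(250/430) = 2.467; 2.467 - 2.394 = 0.073; Phi(0.073) = 53%. Redness at 25: 3.236 x sqrt(25/27) = 3.113; 3.113 - 2.394 = 0.719; Phi(0.719) = 76%.

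**All three together.** At 430 and 250 per group redness is almost certain to be significant, so joint power is set by cells and flare.

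| Per group | Alpha each | rho 0 | rho 0.5 | rho 0.7 | rho 0.9 | rho 1 |
|---|---|---|---|---|---|---|
| 430 | 0.0167 | 64% | 69% | 71% | 75% | 80% |
| 430 | 0.05 | 81% | 83% | 85% | 87% | 90% |
| 250 | 0.0167 | 28% | 36% | 40% | 46% | 53% |
| 250 | 0.05 | 48% | 55% | 58% | 63% | 69% |

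Check at rho 0 and 430 per group: 0.802 x 0.800 = 0.642 at 0.0167, and 0.900 x 0.899 = 0.809 at 0.05.

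**One site, 25 per group.** At 0.05 each, cells and flare have about 12% power apiece, and about 1% (rho 0) to 8% (rho 0.9) jointly.

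**Size for 80% joint power.** With the split: 545 per group at rho 0, 474 at rho 0.9, and 430 only at rho 1. Without the split, 423 per group is enough even at rho 0.

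**The case against.** The strongest reply is that the calculation is coherent as it stands. If the plan intends three separate claims, with family-wise error held at 5% and at least 80% power for each, then 0.05/3 with the largest of the three sizes is the right calculation, and 430 per group delivers it. Section 13.1's set of tests and section 13.3's adjusted p-values fit that reading, and the sentence about wanting a difference on the three outcomes explains a choice of size rather than defining success. This stands. A reader might infer that the split is an error, or that the plan promises 80% for an all-three success rule and breaks the promise. The documents do not support that, because they contain no success rule. What they do contain is an aim, stated twice, that the quoted 80% does not describe.

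Two further objections also stand. First, the shortfall depends on an unknown correlation: 16 points at rho 0, 5 at rho 0.9, none at rho 1. Second, nobody plans to recruit 430 per group. A reader might conclude that dropping the split restores 80% at no cost in patients, but 430 per group means 860 patients, 360 more than the planned 500 even if all sites were pooled.

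Finally, 860 by group, taken literally, would give 97-98% for all three with the split (rho 0 to 0.9), and the shortfall would vanish. The table contradicts that figure and no section plans to recruit it, so 430 is used here.

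**Conclusion.** The point holds in a limited form. The 80% in section 13.2 is a per-outcome figure attached to an all-three aim. At 430 per group the matching joint power is about 64% to 75% for correlations of 0 to 0.9. This rests on three assumptions: the table's sizes are correct, the normal approximation holds, and the correlation lies in that range. The firm defect is the missing decision rule; the size of the shortfall is conditional. It is also smaller than the gap between the 430 per group calculated and the 25 per group per site that section 13 says will be analysed alone, where cells and flare have about 5% power each whatever is decided about the joint claim. The correction is worth making because it is cheap and because no power figure, pooled or per site, can be interpreted until the rule is fixed.

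**What to change.** State one decision rule in sections 13.2 and 13.3, with the power that goes with it.

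- **(a) Three separate claims.** Keep 0.05/3, or use Holm; say that 80% is per outcome; remove the implication that it covers all three together.
- **(b) All three required.** Test each at two-sided 0.05 without a split and quote joint power: 81-87% at 430 per group for correlations 0 to 0.9, with the correlation declared as an assumption.

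The choice belongs to the investigators. Option (b) has a real cost: redness alone would no longer be success. In a within-centre analysis of 25 per group, the requirement on cells and flare would be met only about 1-8% of the time, against about 76% power for redness alone at 0.0167.

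Under either option, correct 0.5/3 to 0.05/3, reconcile 860 by group with the table's 430 by group, and report power at the planned sizes:

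- **250 per group, if pooled:** with the split, 53% for each of cells and flare and 28-46% for all three; 48-63% for all three without it.
- **25 per group per site:** about 5% for each of cells and flare with the split.

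This is a wording change. Section 13.6 has the final statistical plan agreed before data lock and any analysis, which is the latest point at which to make it.

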12.3. Data Management

In this study, an electronic case report form (eCRF) within the RedCap platform will be used for data capture. For each surgical center, a different RedCap database will we created, allowing only access to the corresponding investigator and CRO (in case assigned by the CTC). Hence, there will be no sharing of data between the different surgical centers. Also, the data of the different centers will not be pooled for comparison between the centers, only comparison within each center will be performed (see section statistical analysis). Hence, during the whole trial there will be a strict separation of study data between each center.

All documents will be stored safely in confidential conditions. On all clinical investigationspecific documents, other than the signed consent, the participant will be referred to by the clinical investigation participant number/code, not by name.

All clinical investigation documentation will be kept for 10 years from the clinical investigation plan defined end of clinical investigation point. When the minimum retention period has elapsed, clinical investigation documentation will not be destroyed without permission from the sponsor.

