13. STATISTICS

General comment: for the statistical analysis, a comparison will be made between both study arms included *in each center*. Hence, there will only be a comparison between both study arms in each site. No pooling of the data from the different sites will be performed nor will there be a comparison between the different study sites.

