13.1. Description of statistical methods

Missing data handling

The missing processes was described by Rubin (1987) who made a distinction between (a) Missing Completely At Random (MCAR), (b) Missing At Random (MAR), and (c) Missing Not At Random (MNAR)¹. We will test with the statistical test of Jamshidian and Jalal (2010), implemented in the MissMech R Package (Jamshidian et al., 2014), whether missing data were MCAR. If they are not MCAR, we will investigate whether or not the missing mechanism could be explained by baseline characteristics (eg, sociodemographic, medical features) of patients using logistic regression, which would suggest an MAR mechanism. If missing data are not MCAR or MAR, they will considered as MNAR. As indicated by Molenberghs et al. (2008) one can never totally exclude a MNAR process, but every MNAR model has an MAR counterpart with equal fit. Therefore, in case of MCAR, MAR, or MNAR missing processes, maximum likelihood (ML) and multiple imputation (MI) were used, using the mice R package for the last one (Raghunathan et al. (2001) ; van Buuren & Oudshoorn (2016)) with a predefined seed. Indeed, ML and MI use all available data in the study and produce unbiased estimates of the treatment effect and correct P values. MI is also a method of choice because it allows not only to impute missing values on the outcome but also on the covariate (Dziura, 2013) and is valid for MCAR, MAR, and MNAR. (Molenberghs et al. (2008)) Molenberghs and Kenward (2007) recommended ML estimation without imposing a structure on the covariances among the repeated measures.

Analysis of primary outcomes

The primary outcomes will be analysed by a set of Wilcoxon-Mann-Whitney tests, but complementary tests will be done using mixed models for ordinal data (Hedeker & Gibbons, 2006) to take the multicenter nature of this trial into account. It is likely that patients in the same centre will tend to have correlated outcomes, meaning that they are more similar to other patients recruited within the same centre that to patients: same clinical care paths within centres will be observed, medical centre having their own medical practice preferences, and, therefore, the independence assumption underlying classical statistical tests is likely to be violated. We will therefore take this correlation between the patients of a same centre into account by using mixed models with the centre included as random effect for continuous outcomes (Chu et al., 2001; Kahan &

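### Section 13.2 calculates 428 to 430 patients per group for cells and flare, then recruits 25 per group per site without stating power, which within a site is about 5% for each of these two outcomes

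*Combined protocol and SAP*

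**What the plan says.** Section 13.2 gives the design target: "The target p-value was 0.5/3 (=0.0167) in order to correct for multiple testing, and the power was set to 80" per cent. From pilot data it tabulates the size needed for each primary outcome with a Wilcoxon-Mann-Whitney test:

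- cells: 428 per group, 858 in total
- flare (tyndall): 430 per group, 860 in total
- redness: 27 per group, 54 in total

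The rule for choosing among them is: "Because we want to see a difference on the three outcomes, we choose the highest sample size estimation". The text then concludes that "a total of 860 patients would be required by group in order to show a difference between 23G and 27G". The section ends: "For each surgical site 25 patients will be recruited by group (i.e. 50 patients will be included at each site". Section 8.1 sets 500 patients in all, with up to 50 per site.

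On the unit of analysis, section 13 says: "No pooling of the data from the different sites will be performed". Section 12.3 says that "only comparison within each center will be performed" and gives each site its own database. Section 5 also describes the comparison as one made inside each centre. In section 13.1, "The primary outcomes will be analysed by a set of Wilcoxon-Mann-Whitney tests", but "complementary tests will be done using mixed models for ordinal data", with centre as a random effect. Sections 5 and 11.1 allow the larger gauge to be 23G or 25G. Section 13.3 sets 5% two-sided significance with adjustment for multiple comparisons, and names no method.

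**The concern.** The section calculates one size and recruits another, with nothing to connect them. For redness the difference is trivial (27 against 25). For cells and flare it is 430/25 = 17.2-fold. Because only within-site comparison is allowed, the primary tests compare 25 patients with 25. The only power figure in the plan, 80%, belongs to the calculated sizes.

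Cells and flare carry the intra-ocular inflammation part of the primary endpoint in section 6.1. If a site's tests on them have little chance of success even when the pilot effect is real, a non-significant result says little about that effect. A reader who sees 80% in 13.2 might still take it as evidence of no difference in inflammation. The stated wish for a difference on all three outcomes is affected most, since it depends on the weakest of the three.

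**Working it through.** **Inputs.** From 13.2: alpha 0.0167 (that is, 0.05/3), power 80%, and n0 = 428, 430 and 27 per group. From 13.2 and 9.3: 25 per group per site, allocated 1:1. From 8.1: 500 in total, or 250 per group. Two-sided testing is stated in 13.3 for the analyses; I assume that it also held for the calculation.

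**The plan's own figures.** The table cannot be rebuilt from raw inputs, because the pilot percentages by grade are not given. The row totals can be checked: 2 × 430 = 860 and 2 × 27 = 54 agree, but 2 × 428 = 856, where 858 is printed. Also, 0.5/3 = 0.167, whereas 0.05/3 = 0.0167.

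**Scaling.** For fixed grade percentages, the required size is proportional to (z for alpha/2 + z for power)². The stated size, alpha and power therefore fix the standardised effect:

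- noncentrality at n per group = (2.394 + 0.842) × √(n/n0) = 3.236 × √(n/n0)
- power = Φ(noncentrality − z) + Φ(−noncentrality − z), where z = 2.394 at 0.0167 and 1.960 at 0.05

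At n = n0 this returns 80% by construction, so it is a calibration and not an independent reproduction.

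**Within a site, 25 per group.**

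- Flare: 3.236 × √(25/430) = 0.780. Power at 0.0167 = Φ(−1.614) + Φ(−3.174) = 0.053 + 0.001 = 5.4%. At 0.05 = Φ(−1.180) + Φ(−2.740) = 0.119 + 0.003 = 12.2%.
- Cells: 3.236 × √(25/428) = 0.782, with the same power to one decimal.
- Redness: 3.236 × √(25/27) = 3.114. Power at 0.0167 = Φ(0.720) = 76.4%.
- All three together: no more than the smallest single-outcome power, so at most about 5% at 0.0167 (about 12% if each were tested at 0.05).

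**Check by simulation.** I used the tie-adjusted Wilcoxon-Mann-Whitney sample size formula, assumed several ordinal grade distributions, tuned the shift between groups to give a total of 860 or 54, and simulated tie-corrected tests (20,000 to 60,000 runs).

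- At 430 per group and 0.0167, power was 80.1 to 80.5%, so the calibration is sound.
- Cells and flare, 25 per group, 0.0167: 4.8 to 5.2% for moderately spread five-grade distributions, 4.0% with 80% of eyes in the lowest grade, and 2.8% with 85% there. At 0.05: about 12% throughout.
- Redness, 25 per group, 0.0167: 79 to 84%. Square-root scaling understates power a little for so large an effect, so 76 to 84% is the fair range.

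**Other readings of 13.2**, for cells and flare at 25 per group (0.0167, then 0.05). If calculation and test were both one-sided: about 8% and 18%. If the requirement were really 860 per group: about 3% and 8%. If the design alpha were really 0.167: about 3% and 8%.

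**All 500 combined.** This is simple two-group scaling with ten full sites (500/50 = 10), no centre effect and the pilot effect at every site. Noncentrality = 3.236 × √(250/430) = 2.467, and power at 0.0167 = Φ(0.073) = 53%. At 0.05 it is 69%.

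**The case against.** Four points can be made for the plan.

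First, nothing is hidden. The 430 and the 25 stand in the same short section, and no sentence claims 80% power for 25 per group. That is right: what is missing is a reason for the recruited size and a power figure for it.

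Second, redness is adequately sized. That also stands. A reader might infer that every primary outcome is badly underpowered, but the documents do not support this: at 76 to 84%, redness is close to target before missing data.

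Third, the mixed models in 13.1 could use all sites. They are called complementary, however, and they need the cross-site data that sections 12.3 and 13 rule out. Even if they are kept, 500 is below the calculated 860. The 53% is a rough guide under favourable assumptions and is not the power of the ordinal mixed model itself.

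Fourth, the exact percentages rest on pilot data not shown and on an assumed two-sided calculation. This limits precision: about 3 to 5% two-sided, or about 8% one-sided. Every reading tried leaves adjusted within-site power below 10%, so the conclusion is unchanged.

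**Conclusion.** The concern holds for cells, for flare and for the joint aim. Section 13.2 chooses the largest calculated size and then recruits a seventeenth of it per site, in a design that compares arms only within sites, and gives no power for that size. Assuming a two-sided calculation, complete data and the pilot 23G versus 27G effects, within-site power at 0.0167 is about 5% for each of cells and flare (3 to 5% across assumed grade distributions; about 12% at 0.05), about 76 to 84% for redness, and at most about 5% for all three together. At sites that compare 27G with 25G the pilot effects need not hold, and power is lower if the true effect is smaller.

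A reader might also infer that the trial must enrol more patients. The documents do not force that. A small sample per site can be a deliberate choice, provided the plan says what it can and cannot show.

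**What to change.** No patients or procedures are added. Section 13.6 foresees a final statistical plan agreed before data lock and before any analysis, so the changes can be made there and in 13.1 and 13.2.

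1. In 13.2, after the sentence on 25 per group, give the within-site power at two-sided 0.0167: about 5% for cells and for flare (3 to 5% depending on the grade distribution), about 76 to 84% for redness, and at most about 5% for all three jointly. State the assumptions (pilot 23G versus 27G effects, two-sided calculation, complete data). Say that 80% applies to the calculated sizes and is not delivered within a site for cells, flare or the three jointly, and that the figures need not hold where the comparator is 25G.
2. In the same section, change the requirement to 430 per group (860 in total), change 0.5/3 to 0.05/3, and check the total for cells (856 or 858).
3. In 13.1, keep the three primary outcomes and the planned tests. Add an effect estimate with a 95% confidence interval for each outcome, and a statement that a non-significant within-site result for cells or flare will not be read as no difference.
4. Reconcile the no-pooling rule (sections 5, 12.3 and 13) with the cross-centre mixed models (13.1). If the models are kept, state that 500 is below the calculated 860 and that combined power for cells and flare is roughly 53% at 0.0167 by simple two-group scaling, assuming ten full sites, no centre effect and the pilot effect at every site.

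The cost is a less favourable power statement and one decision on pooling. Keeping the mixed models would also need a planned transfer of data from the separate site databases.

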13.3. The level of statistical significance

For all analyses, the level of significance will be 5% two-sided significant level. P-values will be adjusted for any multiple comparisons in order to maintain an overall type I error rate of 5%.

13.4. Criteria for the termination of the clinical investigation

Clinical investigation will be terminated 1 week post-op.

13.5. Procedure for accounting for missing, unused and spurious data

Missing data will be reported with reasons given where available, and the missing data pattern will be examined. We will explore the mechanism of missing data by means of logistic regression models which will explore if missingness (i.e. whether the primary outcome is missing or not) is related to measured baseline variables. Covariates found to be predictive of missingness will, where appropriate, be included as a covariate in the analysis model.

